1.0 SYNOPSIS

1.1 Design

This will be a prospective multi-center single arm open-label pilot study of oral glyburide in patients with acute traumatic cervical spinal cord injuries (SCI). The study population consists of subjects with acute traumatic ASIA A, B or C SCI, age 18-80 years, and able to start study drug within 8 hours of injury. The study will enroll and treat up to a maximum of 10 patients who will be matched in a 1:3 ratio with historical controls collected from the North American Clinical Trials Network database.

1.2 Objectives

Primary Objectives

- To assess the feasibility of recruiting subjects with ASIA A, B, or ASIA C acute SCIs within the specified 8-hour time frame.
- To assess the preliminary safety of oral glyburide in subjects with ASIA A, B, or ASIA C acute ACIs

Secondary Objectives

- To study the pharmacokinetics of oral glyburide following acute SCI.
- To undertake a preliminary assessment of the effects of study drug on measures of neurologic outcome using a matched cohort group for comparison.
- To study the effects of study drug on serum biomarkers.
- To study the effects of study drug on intramedullary MR imaging changes related to SCI.

1.3 Interventions and Duration

Standard of care treatment will be instituted for all patients including management of respiratory and hemodynamic parameters in a monitored setting for at least the first three days following SCI. All subjects meeting eligibility criteria will be approached as soon as possible following injury and informed consent obtained for enrollment. While all subjects will undergo standard of care computed tomography (CT) and magnetic resonance imaging (MRI) studies, only review of the CT studies will be required prior to enrollment.

As soon as feasible and if indicated, surgical intervention for spinal cord decompression and spinal stabilization will be undertaken. Safety labs and Adverse Events will be assessed through Day 14 or discharge (whichever is earlier). Serum biomarker levels will be assessed at baseline, and Days 1, 3, and 7. Adverse events will be further assessed, along with functional outcomes, at Day 28 (± 7 days), Day 42 (± 7 days), Day 84 (± 14 days), Day 182 (± 14 days), and Day 365 (± 30 days). Study participation is expected to last 365 Days ± 30 days. Adverse Event and functional outcome assessments will be undertaken by ASIA-certified study personnel.

1.4 Statistical Considerations

Descriptive statistics will be generated for all variables of interest. Categorical measures will be reported with frequencies, percentages and continuous measures with means and standard deviations.

The primary outcomes of feasibility will be the rate of recruitment and the proportion of patients recruited versus screened.

All adverse events that occur during the initial hospitalization period will be summarized. The frequency of adverse events during this period will be compared to matched NACTN Registry historical controls in a 1:3 ratio (along with corresponding confidence intervals).

Matched tests will be utilized to compare neurologic outcomes and biomarker levels between enrolled subjects receiving oral glyburide and matched historical controls.

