Between August 2015 and August 2016, we screened patients with acute traumatic cervical SCIs (GOSCIP study; clinical trials NCT02524379) for potential treatment with Cirara™. Sixteen patients were screened during this period but none met the eligibility criteria. Given the ongoing enrolment difficulty with this intravenous drug within the 6 hr timeline, we have decided to amend several elements of the trial including some of the inclusion/exclusion

criteria. First, the route of administration will be changed to the oral form allowing for easier and streamlined drug administration. An extension of the window of administration to 8 hours from the time of injury will also be implemented. Several screened patients fell out of the eligibility due to this constrained time window, especially considering that Cirara™ preparation takes in the order of 1-2 hours.

The feasibility of screening, consenting, enrolling, and administering oral glyburide in the acute setting following spinal cord trauma (≤ 8 hours from injury) will be assessed at the participating centers. Further, a comprehensive assessment of all-cause AEs will be undertaken in this study for spinal cord trauma patients.

The data obtained from this pilot study should inform the design of further multicenter phase II/III clinical studies evaluating the efficacy and safety of oral glyburide in improving functional outcomes following SCI.

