3.0 OBJECTIVES

3.1 Primary Objectives

- **Feasibility:** To assess the feasibility of running a larger phase II or III study among this population of patients where treatment must begin within a defined time frame. The number of patients who would otherwise be eligible for the study but did not receive study treatment within the 8-hour time frame will be recorded (ratio of recruited versus screened). The rate of recruitment will also be recorded.
- **Safety:** Vital signs, clinical exams, ECG, and clinical laboratory results will be carefully and continuously monitored during the course of hospitalization. Adverse events (AEs) will be assessed throughout the course of hospitalization through Day 28. In addition to presenting a summary of all AEs, where possible, a comparison of AEs occurring in study subjects vs. those occurring in matched historical controls (as captured in the NACTN registry) will be made. To facilitate this comparison, AEs will be grouped into one of 10 systems according to a modified NACTN chart [20, 21] (see appendix 1): cardiac, pulmonary, hematology, gastrointestinal/genitourinary, infections, skin, failure of stabilization, neuropsychiatric, hypoglycemia/other metabolic, and other. These AEs will be described further with respect to the specific name of the event (that is, the “type” of event; for example, for cardiac events, the type could be bradycardia or other dysrhythmia, cardiac arrest, etc.). Severity (“intensity”, as per the NACTN chart) as well as relatedness to glyburide will also be assessed. The frequency of AEs, as well as mortality (all-cause and cardiac-related), will be compared to that of a matched cohort from the NACTN registry [20, 21].

Specific outcome variables related to assessing blood glucose (BG)-related safety of glyburide are:

- Hypoglycemia (i.e. Blood Glucose (BG) < 55 mg/dL
- Symptomatic hypoglycemia i.e. hypoglycemia with investigator-identified hypoglycemic symptoms.

The following table defines which BG values should be reported as AEs:

Table 1: Blood Glucose Values and AE reporting

BG Value	Report as AE?
70-79 mg/dL	Mandatory AE reporting not required; may be reported as an AE (and coded appropriately in terms of severity) if the event meets the protocol-defined definitions.
55- 69 mg/dL	Must be reported as an AE, if confirmed by a point-of-care or lab value retest (and coded appropriately in terms of severity)

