5.0 STUDY ASSESSMENT AND PROCEDURES

5.1 Screening

Patients with suspected acute cervical SCI will be screened upon arrival to hospital. These evaluations will occur prior to enrolment:

- Vital signs (Temperature, Blood Pressure, Respiration rate, Pulse, O₂ saturation, Height, Weight)
 - Note: Height and Weight can be estimated if patient cannot be measured.
- Physical examination and Medical History
- Cervical SCI Time, Cause, and Level of injury
- Demographics and Clinical Variables (age, race, gender, and BMI)
- Neurological examination including ISNCSCI motor and sensory assessments
- ECG (12-lead), read within 12 hours and recorded as clinically significant or non- clinically significant by study team member
- Clinical laboratory tests:
 - Pregnancy test for women of child-bearing potential
 - Hematology: complete blood count
 - Chemistry: electrolytes (sodium, potassium, chloride, bicarbonate), BUN, creatinine, glucose

- Liver Function Tests: AST, ALT, bilirubin (total and direct), and alkaline phosphatase.
 - Glyburide can commence if liver function tests are not yet available but will be discontinued if ALT > 3 times upper limit or bilirubin > 2 times upper limit of normal.

Because pertinent patient information will already be collected as part of the standard of care, and to reduce additional study-specific procedures, screening and baseline information may be taken from the patient's medical records prior to obtaining informed consent. However, informed consent will be obtained prior to performing any study-specific procedures.

Once study eligibility has been confirmed (inclusion/exclusion criteria are met) and informed consent obtained, the patient will be enrolled into the study.

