7.0 STATISTICAL CONSIDERATIONS

Descriptive statistics will be generated for all variables of interest. Categorical measures will be reported with frequencies and percentages and continuous measures with means and standard deviations. The frequency of AEs will be reported (as captured on the modified NACTN form) and, where possible, will be compared to those of the matched controls (along with corresponding confidence intervals). We will match study patients and the historical NACTN cohort data on criteria including: age, co-morbidities, injury level, and injury severity (ASIA A, B or C SCI). Additionally, the number of patients who were otherwise eligible for the study but did not enroll due to lack of infusion within 6 hours will be reported. Secondarily, matched tests will be utilized to compare neurologic outcomes between those receiving glyburide and matched historical controls.

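### The measure of whether the 8-hour window works is wrongly specified: Section 3.1 equates it with recruited/screened and Section 7.0 ties it to a 6-hour infusion

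*Combined protocol and SAP*

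**What the plan says.** Section 1.2 states the first primary objective as the feasibility of recruiting patients "within the specified 8-hour time frame". Section 4.2 gives the same injury-to-drug time as the specific feasibility reason for enrolling and treating 10 patients.

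Three places then say what will be measured:

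- **Section 1.4:** the primary feasibility outcomes are the recruitment rate and "the proportion of patients recruited versus screened".
- **Section 3.1:** patients who would otherwise be eligible but "did not receive study treatment within the 8-hour time frame will be recorded (ratio of recruited versus screened"; the parenthesis presents the count as that ratio. The recruitment rate is recorded as well.
- **Section 7.0:** the number who were "otherwise eligible for the study but did not enroll due to lack of infusion within 6 hours will be reported".

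The denominator of recruited/screened comes from Section 5.1: "Patients with suspected acute cervical SCI will be screened upon arrival to hospital". That is before eligibility is known. Section 9.1 (Subject Withdrawal) foresees patients who are enrolled but never receive the drug, and gives too little time to prepare and administer it as one example.

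**The concern.** The time window is one of 7 inclusion criteria in Section 4.1. It stands beside 18 numbered exclusions and the CT-based exclusions in Section 4.3. A ratio of recruited to screened absorbs losses on all of these. Low yield because patients arrive or are dosed too late calls for a different phase II/III design response than low yield because eligibility is narrow.

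The documents themselves show that the window is a serious uncertainty. In the preceding intravenous study, "Sixteen patients were screened during this period but none met the eligibility criteria", and Section 2.0 says only that several of them failed on time. Section 5.3 cites a riluzole study whose median injury-to-drug time was 8.5 hours, which the protocol attributes largely to extra MRI. The pilot should therefore produce a clean figure for the window. The count that would supply it is mislabelled in one section and given a conflicting definition in another.

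**Working it through.** The plan has no figure to reproduce. The 10 patients are stated without a formula, precision target or feasibility threshold, and the feasibility analysis is descriptive.

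**Inputs.** Dosed within the window: 10 (Section 4.2, taken as achieved). The number screened, S, and the number of otherwise-eligible patients who missed the window, L, are not in the documents. Both are assumptions here and are varied.

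**Formulas.**
- Recruited/screened = 10/S
- Window success = 10/(10 + L), with L between 0 and S − 10
- Exact (Clopper-Pearson) 95% limits for x of n: the lower limit is the 0.025 quantile of Beta(x, n − x + 1) and the upper limit is the 0.975 quantile of Beta(x + 1, n − x)

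**Step 1: one ratio, many window results.** Take S = 40. Recruited/screened is 10/40 = 25% (12.7% to 41.2%) in every row.

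| L (missed window) | Other failures, 30 − L | Window success | Exact 95% CI |
|---|---|---|---|
| 0 | 30 | 10/10 = 100% | 69.2% to 100% |
| 2 | 28 | 10/12 = 83% | 51.6% to 97.9% |
| 5 | 25 | 10/15 = 67% | 38.4% to 88.2% |
| 10 | 20 | 10/20 = 50% | 27.2% to 72.8% |
| 30 | 0 | 10/40 = 25% | 12.7% to 41.2% |

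For S from 30 to 100 the ratio falls from 33% to 10%. At each S, window success can lie anywhere from 10/S to 100%.

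**Step 2: Section 3.1.** The sentence describes L, a count. Its parenthesis describes 10/S. At S = 40 and L = 5 these are 5 patients and 25%. Neither determines the other.

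**Step 3: Section 7.0 against the rest.**

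| Feature | Section 7.0 | Elsewhere |
|---|---|---|
| Route | infusion | oral (Sections 1.1, 2.0, 5.3) |
| Cutoff | 6 hours | 8 hours (Sections 3.1, 4.1, 4.2, 5.5) |
| Who is counted | patients not enrolled | patients not treated (Section 3.1) |

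Read literally, Section 7.0 counts a reason for non-enrolment that does not arise under the eligibility criteria of this trial.

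**Step 4: enrolled but not dosed in time.** Keep S = 40 and L = 5, and suppose 2 of the 5 had been enrolled. Recruited becomes 12, so recruited/screened rises to 12/40 = 30% although only 10 were dosed in time. Even with its cutoff and route reconciled, a count of patients not enrolled would give 3 instead of 5. Recruited among otherwise eligible would be 12/15 = 80%, against 10/15 = 67% dosed in time.

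**Step 5: the denominator needs a rule.** Consent is an inclusion criterion (Section 4.1), and Section 1.3 has consent sought from patients who meet the criteria. A late arrival would normally not be asked. If L required every other criterion to be met, consent included, and all 5 late patients had never been approached, L would fall to 0. Window success would then read 10/10 = 100% instead of 67%.

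**The case against.** A reader might infer that the trial cannot answer the window question at all. The documents do not support that. Section 3.1 plans to record the otherwise-eligible patients not treated in 8 hours, and Section 7.0 plans to report a count of that kind. Once L is known, 10/(10 + L) follows. The 25% to 100% range describes what recruited/screened shows alone, not what the whole plan would show.

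Other parts of the opposing case also stand:

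- Recruitment rate is a primary feasibility outcome too, so recruited/screened is not the only one.
- Feasibility in Sections 2.0 and 3.1 is wider than the window. It covers screening, consent, enrolment and the running of a larger trial, for which yield per patient screened is a useful planning figure. Demoting it would be a preference, not a correction.
- Section 7.0 is better read as a conflicting version of the count in Section 3.1 than as a separate third measure.
- The values of S and L are illustrative. The 25% end would need every undosed patient with a suspected injury to meet all other criteria, which is unlikely.
- No go/no-go rule uses the ratio, so a wrong phase II/III decision cannot be claimed as a consequence.

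None of this removes the errors of specification. A label equates two different quantities, the statistical section contradicts the trial's own route and cutoff, and patients enrolled but undosed for lack of time can count as recruited.

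**Conclusion.** Wrong as written, in the specification of the window measure. Recruited/screened alone cannot isolate the window: at an assumed 40 screened and 10 dosed, 25% fits window success from 25% to 100%, and from 83% to 50% if between 2 and 10 otherwise-eligible patients are late. The count that could isolate it is planned, but it is mislabelled in Section 3.1, contradicted in Section 7.0, blind there to enrolled patients not dosed in time, and given no denominator or interval. The sizes rest on assumed S and L. The contradictions rest on the text alone. No sample-size or power figure depends on this point.

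**What to change.** 1. Reconcile Section 7.0 with the window and route used in Sections 3.1, 4.1, 4.2 and 5.5.
2. Remove the parenthesis in Section 3.1 that equates the missed-window count with recruited/screened.
3. Keep recruitment rate and recruited/screened. Add as a feasibility outcome in Sections 1.4, 3.1 and 7.0 the proportion dosed within the protocol window among otherwise-eligible patients, with an exact 95% CI.
4. Count patients enrolled but not dosed in time as failures.
5. Count a late patient as otherwise eligible if the criteria that could be assessed at screening are met, without requiring consent or tests not done because the patient was late.
6. Tabulate screen failures by reason. Section 5.3 lists an eligibility worksheet among the documents for registering a patient, so state explicitly that patients who are not enrolled are logged too.

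The cost is wording in three sections and slightly more screening-log work. Sample size and treatment procedures do not change. The estimate will be imprecise: 10/15 = 67% carries an interval of 38% to 88%, and the report should say so.

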2.0 INTRODUCTION

In this initial phase open-label pilot study, we propose to enroll patients with defined inclusion/exclusion criteria at up to ten Level I/II trauma centers including Ohio State University Wexner Medical Center (Principal Site). The primary objectives are to assess the feasibility and safety of enrolling, evaluating, and treating acute cervical SCI patients with oral glyburide.

Oral glyburide is a widely used blood glucose-lowering drug that belongs to the sulfonylurea class. Blood glucose is lowered acutely by stimulating the release of insulin from the pancreas, an effect dependent upon functioning beta cells in the pancreatic islets. Oral Glyburide has been used successfully in the treatment of non-insulin-dependent diabetes mellitus (NIDDM) for more than 20 years. In treating NIDDM, the drug works by inhibiting ATP-sensitive potassium channels in pancreatic beta cells by antagonism of SUR1. This inhibition causes cell membrane depolarization, which causes voltage-dependent calcium channels to open, which in turn causes an increase in intracellular calcium in the beta cell, stimulating insulin release.

The Sur1-Trpm4 channel is selectively expressed in the central nervous system (including the spinal cord) under conditions of ischemia, hypoxia, and trauma [6, 8-10] leading to vasogenic and cytotoxic edema followed by oncotic cell death [11]. A double-blind, multicenter, randomized trial of an intravenous form of glyburide (Cirara™) in patients with large ischemic strokes likely to develop malignant cerebral edema (GAMES-RP study) identified the drug to be well-tolerated at 3 mg per day [2] with few treatment-related serious adverse events (SAEs) reported and reassuringly limited to hypoglycemia.

Neurotrauma patients, including those with spinal cord injuries, typically have elevated blood glucose levels over the first three days following their injury. For example, a large retrospective review of 528 patients with SCI [35] indicated that 53% of patients were hyperglycemic on admission (glucose concentration ≥ 126 mg/dl) and that hyperglycemia was a significant risk predictor of poor functional outcome. As such, oral glyburide administration for its potential neuroprotective effects in the SCI population appears unlikely to cause significant adverse events related to hypoglycemia and may indeed be beneficial independently given its blood glucose lowering effects.

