< 55 mg/dL	Must be reported as a SAE (appendix 2), if confirmed by either a point-of-care or lab value retest (and coded appropriately in terms of severity)

Specific outcome variables related to assessing cardiac-related safety of glyburide are:

- Incidence/severity of cardiac AEs and cardiac mortality
- Incidence of QTc of > 500 ms
- Mean QTc and mean change in QTc from baseline.

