5.8 Days 1-7 (0-168 hours)

- The first dose of glyburide must be administered within 8 hours of injury and stopped after 72 hours. Hard stop rules for glyburide administration are listed below.
- As per recommended standard-of-care guidelines [3], subjects will be admitted to the intensive care unit following initial diagnostic testing where continuous respiratory, cardiac, and hemodynamic monitoring will be undertaken [32]. Maintenance of normal blood oxygenation and a mean arterial blood pressure of 85-90 mmHg will be emphasized in this monitored setting continuously over the first full 7 days following injury.

- The following assessments will be performed through day 7 following injury (during and after study drug regimen):
 - Safety labs: 24 hours (± 12 hours), 48 hours (± 12 hours) 72 hours (± 12 hours) and 96 hours (± 12 hours).
 - Hematology: complete blood count
 - Chemistry: electrolytes (sodium, potassium, chloride, bicarbonate), BUN, creatinine
 - Liver Function Tests: AST, ALT, bilirubin (total and direct), and alkaline phosphatase
 - Blood glucose (BG) monitoring will be hourly (± 30 minutes) for Hours 1-24, every 2 hours (± 30 minutes) for Hours 25-48 and every 4 hours (± 60 minutes) for Hours 49-88. If BG < 70 mg/dL, BG monitoring is required every 15 (± 10 minutes) minutes until BG ≥ 80 for 3 consecutive readings without exogenous bolus glucose supplementation, then hourly (± 30 minutes) for the next 12 hours and every 2 hours (± 30 minutes) thereafter.
 - Continuous bedside cardiac telemetry monitoring from Hour 0 through Hour 72
 - ECG (12-lead) at 4-6 hours, 24 \pm 6 hours, 48 \pm 6 hours and 60-72 hours (from the start of study drug regimen). The ECGs will be read within 12 hours, recorded as clinically significant or non-clinically significant, and signed off on by study team member.
 - Blood sampling for PK prior to dosing, at 4-6 hr (prior to the second study drug administration), 24 \pm 6 hours, 48 \pm 6 hours and 60-72 hours.
 - PK Samples to be drawn as close as possible to ECGs
 - Start time of drug and time of subsequent dosing. Record reason for any missed doses.
 - Concomitant medications and procedures/therapies
 - Review safety and AEs

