- Electrolyte imbalances that are asymptomatic and not considered clinically significant by the investigator should not be reported as AEs even if they are treated; and
- Table 1 in Section 3.1 defines which blood glucose values should be reported as AEs.

Hospitalization, Prolonged Hospitalization or Surgery

Any AE that results in hospitalization or prolonged hospitalization, according to the judgment of the clinical investigator, should be documented and reported as a Serious Adverse Event (SAE).

Neither the condition, hospitalization, prolonged hospitalization, nor surgery are to be reported as an adverse event in the following circumstances:

- Hospitalization or prolonged hospitalization for diagnostic or elective surgical procedures for a preexisting condition. Surgery should not be reported as an outcome of an adverse event if the purpose of the surgery was elective or diagnostic and the outcome was uneventful.
- Hospitalization or prolonged hospitalization required to allow efficacy measurement for the study.
- Hospitalization or prolonged hospitalization for therapy of the target disease of the study, unless it is a worsening or increase in frequency of hospital admissions as judged by the clinical investigator.

6.2 *Evaluating Adverse Events*

All AEs must be evaluated by the Investigators for severity, seriousness, and relationship to Study Drug.

Adverse Event Severity and Seriousness

All AEs will be evaluated by the Investigators separately for both severity (mild, moderate, severe respectively coded as 1, 2, or 3; see appendix 1) and for seriousness (AE versus SAE).

Relationship to Study Drug

The relationship of the AE to glyburide will be specified by the Investigators as either Unrelated, Possibly/Probably related, and definitely related. When considering the potential relationship of an AE, the Study Investigators' assessment will include consideration of the incidence of complications anticipated in the SCI population in the absence of glyburide administration. For instance, in 485 subjects with acute SCIs recruited into the NACTN database, 1376 total complications were recorded during the initial hospitalization (Table 4) [21].

Table 4: Acute care complications: type, frequency, and incidence

Complication Type	Frequency (%)	Incidence Rate (%)
Pulmonary	348 (25.3)	36.7
Infection	285 (20.7)	33.2
Hematology	213 (15.5)	26.6
Cardiac	178 (12.9)	25.6
GI/GU	115 (8.4)	17.1
Skin	113 (8.2)	16.7
Neuropsychiatric	106 (7.7)	19.2

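### Hypoglycemia is not kept out of the matched NACTN comparison of adverse events, although only treated patients are shown to have dense glucose testing and mandatory reporting, so an excess could partly reflect ascertainment.

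*Combined protocol and SAP*

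**What the plan says.** **The comparison.** Section 1.4 plans, for the initial hospitalization: "The frequency of adverse events during this period will be compared to matched NACTN Registry historical controls in a 1:3 ratio". It sets no limit on AE class. Section 3.1 adds: "To facilitate this comparison, AEs will be grouped into one of 10 systems according to a modified NACTN chart". The ten are listed there and include hypoglycemia/other metabolic. Sections 3.1, 4.4 and 7.0 say the comparison is made where this can be done, and 3.1 refers to AEs in controls as the registry captured them. Section 1.4, and the closing sentence of the Section 3.1 safety paragraph on AE frequency and mortality, carry no such qualifier.

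**Glucose in treated patients.** Section 3.1 introduces separate glucose outcomes ("Specific outcome variables related to assessing blood glucose (BG)-related safety of glyburide are"): BG below 55 mg/dL, and symptomatic hypoglycemia. Table 1 sets the reporting rules. For 55-69 mg/dL: "Must be reported as an AE, if confirmed by a point-of-care or lab value retest". Below 55 mg/dL: "Must be reported as a SAE (appendix 2), if confirmed by either a point-of-care or lab value retest". Section 5.8 sets the testing: "Blood glucose (BG) monitoring will be hourly" for Hours 1-24, then every 2 hours to Hour 48 and every 4 hours to Hour 88, with readings every 15 minutes after any value below 70 mg/dL.

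**Controls.** They are matched on age, co-morbidities, injury level and injury severity (Sections 4.4 and 7.0). No glucose testing schedule or reporting rule is given for them. Section 6.2 summarizes 485 registry subjects, in whom "1376 total complications were recorded during the initial hospitalization"; Table 4 breaks this total down.

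**Measure and period.** Sections 1.4, 3.1 and 7.0 compare the frequency of AEs, Section 4.4 their incidence. Section 6.0 has all AEs recorded until the study ends. Note k of Section 5.11 and the end of Section 6.2 have only SAEs newly recorded after Day 28.

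**The concern.** The matched cohort is the planned comparator for one of the two primary objectives, preliminary safety. Hypoglycemia is where a drug effect would be looked for first: Section 2.0 describes the intravenous form as well tolerated, "with few treatment-related serious adverse events (SAEs) reported and reassuringly limited to hypoglycemia".

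A low glucose value with no symptoms becomes an event only if someone measures it and a rule says to report it. Both conditions are met by design in treated patients and are not shown to be met in controls. Matching on age, co-morbidities and injury does nothing about this.

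The qualifiers allow a class to be left out if the registry does not hold it. They do not deal with a class held in both sources but looked for with different intensity. An excess on glyburide in that class could not be divided between drug and testing: a reader might take an artifact for a signal, or dismiss a real signal as an artifact. These data are meant to inform phase II/III design (Sections 2.0 and 10.0).

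**Working it through.** **1. The plan's own registry figure.** Table 4 counts: 348 + 285 + 213 + 178 + 115 + 113 + 106 + 18 = 1376, which reproduces the stated total. Seven systems plus death use it up, so this summary has no separate row for hypoglycemia/other metabolic, failure of stabilization, or other. Hypoglycemia is also absent from the Section 6.2 list of events anticipated without study drug.

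**2. Scheduled glucose readings per treated patient (Section 5.8).** Hours 1-24 hourly: 24. Hours 25-48 every 2 hours: 24/2 = 12. Hours 49-88 every 4 hours: 40/4 = 10. Total 24 + 12 + 10 = 46, before any extra readings. For controls none is stated.

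**3. What unequal capture could do to a hypoglycemia contrast.** Inputs: 10 treated patients (Section 4.2) and 30 controls (1:3). Assumptions not in the documents: the same true risk p in both groups, all treated cases found, and a fraction s of control cases captured. Expected apparent difference = p − p·s. The last column enumerates Fisher's two-sided test exactly, ignores matching, and counts only p < 0.05 with the excess on drug.

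| True risk p | Capture s | Apparent difference | Chance of p < 0.05 |
|---|---|---|---|
| 20% | 100% | 0 points | 1.7% |
| 20% | 50% | 10 points | 10.1% |
| 20% | 0% | 20 points | 32.2% |
| 10% | 50% | 5 points | 4.2% |
| 10% | 0% | 10 points | 7.0% |
| 40% | 50% | 20 points | 18.1% |
| 40% | 0% | 40 points | 83.3% |

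The 50% rows fit the concern better. The 0% rows would require scoring an uncollected class as zero events, which the qualifiers give reason not to do.

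**4. Dependence on the interval method.** The plan names no method or confidence level. For 2/10 versus 0/30, the Newcombe 95% CI for the difference is 1.7 to 51.0 points and excludes zero, yet Fisher p = 0.058. For 1/10 versus 0/30 the interval is −4.0 to 40.4 points (p = 0.25). These also ignore matching.

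**5. Any all-AE total.** Registry mean: 1376/485 = 2.84 events per patient; × 10 = 28.4 expected in 10 patients at that rate. Each event found only through trial procedures adds 1/28.4 = 3.5%. If 2 patients had 1 to 3 such events each (assumption), the total rises by 2/28.4 = 7.0% to 6/28.4 = 21.1%. The 485 are all acute SCIs, so the base for matched cervical controls may differ.

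**6. Which measure.** Table 4 prints both. Pulmonary: 100 × 348/485 = 71.8 events per 100 patients, against 36.7% of patients affected. Event counts and patients affected are thus clearly different quantities, and repeated glucose values inflate the first more easily than the second.

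**7. Treated-only reporting.** Exact (Clopper-Pearson) 95% CIs: 0/10, 0 to 30.8%; 2/10, 2.5 to 55.6%.

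**The case against.** The best defense is that the plan already limits itself. Section 3.1 names its ten systems, so it would be wrong to say that the classes are unspecified. Its body text compares only where this can be done, against what the registry captured. On the ordinary reading, a class the registry does not hold is not compared. This stands for non-capture. It does not cover a class that is captured but sought less intensively.

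A reader might infer from step 1 that the registry does not record hypoglycemia at all. The documents do not support that. Table 4 is a published summary, used in Section 6.2 to help judge relatedness. It also lacks a stabilization row, although construct failure, loss of reduction and failure of orthosis are on the anticipated-events list that points to Appendix 1. That appendix and the registry form were not available.

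A reader might also infer that an all-AE total is planned. None is explicitly stated, so step 5 is conditional.

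A third tempting reading is that monitoring to Day 14 or discharge (Sections 1.3 and 6.2) contradicts 28 days in Section 4.4. Sections 1.3 and 6.2 both add a Day 28 review, so these fit together. Only Section 6.0 conflicts with Sections 5.11 and 6.2.

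Further points in the plan's favor:
- The two glucose outcomes are already separate, and relatedness is rated. This helps with single events but does not correct a group contrast.
- Section 2.0 expects few hypoglycemia-related events.
- The bias would overstate harm, not hide it.
- Frequency can be read as patients affected, since categorical measures get frequencies and percentages. The wording does not settle it.
- Section 10.0 asks for cautious interpretation.

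**Conclusion.** The point holds as one of specification and interpretation. As written, hypoglycemia may enter the registry contrast with 46 scheduled readings and mandatory reporting on one side and nothing stated on the other. An excess there, or in any total that includes it, could be partly ascertainment. How much cannot be derived from the documents: the 5- to 20-point apparent differences at half capture rest on assumed risks of 10% to 40%.

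Unequal ascertainment is itself inferred from what is shown for treated patients and not shown for controls. If the registry form shows comparable testing and reporting, the concern falls away for this system.

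The same question applies, less sharply, to cardiac events. Section 5.8 gives treated patients scheduled ECGs and telemetry to Hour 72, which may raise cardiac capture.

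The conflict over new non-serious AEs after Day 28 is real, but it touches the hospital-period comparison only for stays longer than that. Overall priority is low to moderate for a descriptive 10-patient pilot; the design is not invalidated.

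**What to change.** 1. In Sections 1.4, 3.1 and 7.0, report hypoglycemia for treated patients only, with exact CIs. Leave it out of the between-group contrast and of any all-AE total unless the registry is shown, before control outcomes are extracted, to have ascertained it comparably. The test should be comparable testing and reporting; a field on the registry form is not enough. Apply the same check to the other nine systems, with a note on cardiac events, and list those that pass.
2. In Sections 1.4, 3.1, 4.4 and 7.0, make the compared measure the number of patients with at least one event per system during the initial hospitalization. Name a CI method that respects the 1:3 matched sets, and give event counts as secondary.
3. Reconcile Section 6.0 with Section 5.11 note k and Section 6.2 on when recording of new non-serious AEs ends.

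The cost is rewording and one check of the registry's form and procedures; no new patient data are needed. The small downside is that hypoglycemia would then have no comparator and would be read from the wide intervals in step 7.
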